11.2.2 Randomization

Patients will be randomized in a 1:1 ratio using permuted blocks with random block sizes. Randomization will be stratified by center and by NYHA class. Randomization schedules will be generated by a Medtronic statistician using computer-generated random numbers.

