11.5.1 Secondary objectives

To assess all-cause mortality in the aCRT ON arm compared to aCRT OFF.

Mortality will be illustrated with Kaplan-Meier graphs. A Cox proportional hazards regression model will be used to estimate the HR of aCRT compared to control, which will be reported with its p-value and 95% confidence interval. The model will include the stratification variables also included in the primary objective model.

To assess the rate of intervention for heart failure decompensation for aCRT ON compared to aCRT OFF.

Incidence of intervention for heart failure decompensation will be illustrated with cumulative incidence graphs. A Cox regression model will be used to estimate the cause-specific HR of aCRT compared to control, which will be reported with its p-value and 95% confidence interval. The model will include the stratification variables also included in the primary objective model. Additionally, recurrent event survival analysis will be performed to compare rates of interventions for heart failure decompensation.

To test the hypothesis that aCRT ON increases the proportion of patients that improve on the Clinical Composite Score (CCS) compared to aCRT OFF, at 6 months of follow-up.

The Clinical Composite Score classifies patients according their clinical status at 6 months post randomization into categories Improved, Unchanged, and Worsened²². A patient is classified Worsened in case of death, hospitalization for worsening heart failure, worsened NYHA class (using last observation carried forward), or worsened status on the Global Assessment Score. Also patients that exit the study or cross over because of worsening heart failure are classified Worsened. A patient is classified Improved when not Worsened and there is an improvement in NYHA class or Global Assessment Score. Patients that are not Worsened or Improved are Unchanged.

The proportion of patients who Improved will be compared between the arms of the study with a logistic regression model, correcting for the stratification variables also included in the primary objective model.

To test the hypothesis that aCRT reduces the incidence of AF compared to aCRT OFF.

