3 RATIONALE FOR STUDY DESIGN

The study design and rationale can be found in the CIP. AdaptResponse is a prospective, randomized, controlled, interventional, single-blinded, multi-center, post-market, global Cardiac Resynchronization Therapy (CRT) in heart failure (HF) clinical study. The purpose of this clinical study is to test the hypothesis that market released CRT devices which contain the AdaptivCRT® (aCRT) algorithm have a superior outcome compared to standard CRT devices in CRT indicated patients with normal atrio-ventricular (AV) conduction and left bundle branch block (LBBB).

Following enrollment and baseline assessment, eligible subjects will be implanted with a CRT system containing the aCRT algorithm and randomized in a 1:1 fashion to either treatment (aCRT ON) or control (aCRT OFF) groups. **aCRT ON** means CRT therapy with ambulatory optimization and preferential LV-only pacing; **aCRT OFF** means standard bi-ventricular CRT therapy. The randomization will be stratified by two factors: site and NYHA class at enrollment. The primary objective is to compare the incidence of the combined endpoint of all-cause mortality and intervention for heart failure decompensation between the aCRT ON and aCRT OFF groups. Because the event rate is expected to be relatively low, the study utilizes an “event-driven” design that requires a review of accumulating endpoint events during the trial to possibly modify enrollment goal and follow-up duration in order to maintain study power. Study subjects will be followed until the required number of endpoint events is reached and/or a decision by Medtronic, Ethics Committee, or regulatory authority, whichever occurs first.

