where TtoHFevent starts from the date of randomization and ends at the date that the first HF event occurs for those who experience the HF event, or the date of death for those who died before experiencing a HF event, or the date of last documented follow-up for those who are censored. HFeventCens = 0 when a subject did not experience a HF event or death and therefore was censored; HFeventCens = 1 when a subject experienced a HF event the first time since randomization; HFeventCens = 2 when a subject died without experiencing a HF event. The competing risk exists when HFeventCens = 2.

The hypothesis regarding the aCRT effect on HF event will be tested using a Cox proportional hazards regression model with a random site effect (frailty), stratified by NYHA class at enrollment. Section 4.3.2 has described this model in details. The analysis will be conducted using code similar to:

```
PROC PHREG DATA=HFevent;  
  CLASS NYHA site;  
  MODEL time*HFevent(0) = rand / TIES=efron;  
  STRATA NYHA;  
  RANDOM site/dist = gamma;  
RUN;
```

In these codes, HFevent = 1 if a subject experienced a HF event and HFevent = 0 otherwise; time to HF event starts from the date of randomization and ends at the date that the first HF event occurs for those who experienced at least one HF event, or the date of last documented follow-up or date of death for those who are censored. Date of last documented follow-up since randomization is the maximum value among the dates of randomization, randomization programming, any study scheduled follow-up visit, exit, adverse event onset, adverse event resolved, system modification, and healthcare utilization.

The model assumptions will be checked using the same methods that are described in detail in section 4.3.2 for the primary endpoint. That is, the assumption of proportional hazards between the treatment arms will be checked by testing the significance of treatment by time interaction term; and, the assumption of constant hazard ratio for treatment across NYHA classes will be checked by testing the significance of treatment by

NYHA class interaction and evaluating the hazard ratio for treatment within each NYHA class.

Missing Data

Non-informative censoring is assumed for lost to follow up in the analysis of intervention for heart failure decompensation

Secondary Competing Risk Analysis: Fine-Gray Regression

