The process of ancillary analysis for intervention for heart failure decompensation follows similar rules as those for the primary endpoint. NYHA class at enrollment will be regarded as a covariate instead of a stratification factor in this ancillary analysis. Thus, the entire process will be based on frailty models. In the beginning the effect of each subject characteristic on intervention for heart failure decompensation will be tested in a univariate frailty model using codes similar to the below:

```
PROC PHREG DATA= HFevent;  
  CLASS site SubjCha; * CLASS only if SubjCha is categorical;  
  MODEL time* HFevent(0) = SubjCha / TIES=efron;  
  RANDOM site/dist = gamma;  
RUN;
```

After that, the final multivariate Cox regression model will be determined from the full model using backwards selection. Note the backwards selection will be performed manually because the SAS PHREG procedure ignores the SELECTION option for the frailty model analysis.

Analysis of Recurrent HF Events

In this analysis, the incidence of intervention for heart failure decompensation will be summarized and compared between the two treatment arms using a multistate Markov model. This model is also referred to as a stratified Andersen-Gill model.¹⁷ This model was recommended because it allows a flexible modelling strategy that incorporates important features in the analysis of intervention for HFdecompensation and death and in the meantime extends relevant characteristics of other models for analysis of recurrent events.¹⁸ Stratification of NYHA class and random center effect will not be considered in this analysis.

The multi-state model stratifies a Cox model by transition states as follows.

$$\alpha_k(t | X) = \alpha_{k_0}(t) \exp(X' \beta)$$

for covariates X, time t and transition states from k = 1, ..., K.

These transition states include first intervention for HF decompensation, second intervention for HF decompensation, etc., death, death after first intervention of HF decompensation, death after second intervention for HF decompensation, etc.

The dataset should be arranged similar to:

PTID	Time1	Time2	Transition	Status	trtGroup
M0000001	0	60	R->H1	0	1
M0000001	0	60	R->D	0	1
M0000002	0	14.2	R->H1	1	2
M0000002	0	14.2	R->D	0	2
M0000002	14.2	60	H1->H2	0	2
M0000002	14.2	60	H1->D	0	2
M0000003	0	24.7	R->H1	0	2
M0000003	0	24.7	R->D	1	2
M0000004	0	38	R->H1	1	1
M0000004	0	38	R->D	0	1
M0000004	38	48.5	H1->H2	0	1
M0000004	38	48.5	H1->D	0	1

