In this dataset (which will be referred to as mmsurvdata),

- The following definitions apply:
 - Time1 and Time2 are the start and end time of a period at risk for an event, which can be either a HF endpoint or a censoring event
 - The events being modeled are Randomization (R), first intervention for HF decompensation (H1), second intervention for HF decompensation (H2) and Death (D)
 - A subject from R can transition to H1 (R->H1) or D (R->D) and a subject from H1 can transition to H2 (H1->H2) or D (H1->D)
 - Status indicates whether a possible transition occurred (Status=1) or no longer at risk to present transition (Status=0)
 - trtGroup indicates whether the subject is aCRT ON (trtGroup =1) or aCRT OFF (trtGroup =2)
- The subject histories in the example dataset shown above were as follows:
 - Subject M0000001 made it 60 months with no intervention for HF decompensation or death
 - Subject M0000002 had an intervention for HF decompensation at 14.2 months and made it the remainder of the 60-month follow-up with no additional intervention for HF decompensation nor death
 - Subject M0000003 died at 24.7 months without a prior HF event
 - Subject M0000004 had a HF event at 38 months and had accrued 48.5 total months of follow-up

The definition above accounts for up to two HF events. For the actual analysis, the breadth of transition events will be dependent on the data. The value N for

H[N-1]->H[N]

where N is the maximal number of HF events modeled, will require that an adequate number of subjects experience at least N HF events. The definition of adequate will be guided by the data, but will ultimately be left to the discretion of the analysts.

R code for implementing the multistate Markov model will be similar to:

```
> library(survival)
> fit1 <- coxph(Surv(time1, time2), status) ~ factor(trtGroup) + cluster(pt) +
strata(transition), data= mmsurvdata)
> print(cox.zph(fit1))
```

Determination of Patients/Data for Analysis

Again, the primary, subgroup and ancillary analysis for intervention for HF decompensation will follow the ITT principle and include all randomized patients; while sensitivity analysis will only include randomized patients with ECG Core Lab confirmed LBBB.

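### The supportive recurrent HF-event model leaves out NYHA class, a randomisation factor, which pulls the hazard ratio slightly toward 1 if aCRT has a true effect

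*SAP*

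**What the plan says.** SAP section 3 gives the design: "The randomization will be stratified by two factors: site and NYHA class at enrollment". Protocol 11.2.2 agrees: "Randomization will be stratified by center and by NYHA class".

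For secondary objective #2, SAP 4.4.2 has the hypothesis "tested using a Cox proportional hazards regression model with a random site effect (frailty), stratified by NYHA class at enrollment". Within the same objective, the Fine-Gray model, the two sensitivity models and the subgroup model are also stratified by NYHA class, and the covariate-adjusted analysis treats it as a covariate.

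The recurrent-event model, a Cox model stratified by transition, is the exception: "Stratification of NYHA class and random center effect will not be considered in this analysis". Its R line matches, with "factor(trtGroup) + cluster(pt" and transition strata but no NYHA term.

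Protocol 11.5.1 says of the HF-event Cox model: "The model will include the stratification variables also included in the primary objective model". It then adds: "Additionally, recurrent event survival analysis will be performed to compare rates of interventions for heart failure decompensation". It names no covariates for that further analysis. SAP Table 2 (section 4.1.3) schedules the recurrent analysis for the interim DMC reports and the final report.

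**The concern.** NYHA class is a randomisation factor and an inclusion criterion, so it should be on file for every randomised patient. SAP 4.3.6 lists it among the predictors expected in the final risk model. Leaving a prognostic factor out of a Cox model attenuates a non-null hazard ratio. A multistate model adds a second route. The risk sets after a first HF event are selected on that event, so if aCRT works, randomisation no longer balances NYHA class between arms in the later transitions.

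Software does not explain the choice. SAP 4.3.4 drops the site effect from the as-treated Cox model so that a sandwich variance can be used, but keeps the NYHA strata. The Fine-Gray model in 4.4.2 likewise drops centre and keeps NYHA class.

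At stake is a modest understatement of the effect on repeat HF interventions. SAP 4.2 has the DMC weigh evidence on objective #2 when it considers early stopping.

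**Working it through.** **The plan's own figure.** No power is stated for the recurrent analysis; the stated figure is 1100 primary events. The fixed-design formula 4(z₀.₉₇₅ + z₀.₉₀)²/(ln HR)² at HR 0.81818 gives 4 × (1.960 + 1.282)²/0.2007² ≈ 1044. A four-look O'Brien-Fleming-type design with efficacy and futility stopping inflates this by 1.057, to about 1104. Exponential accrual then needs 2873 patients (stated 2874; 75% event-free at 2 years, 3 + 2.25 years) or 3324 (stated 3326; 85%, 4 + 3.5 years). The design inputs are therefore understood.

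**Inputs from the documents.** 3500 patients, 1:1, balanced on NYHA class; control arm 85% event-free at 2 years; 4 years of accrual plus 3.5 years; true HR 0.82, applied to every transition.

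**Assumptions not in the documents.** NYHA II/III/IV mix 50/45/5% (50/40/10% in the last row); the NYHA hazard ratios shown; deaths 30% of events; hazard doubled after a first HF event; up to three HF events plus death. Loss to follow-up was not modelled.

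**Method.** The SAP's model (one treatment coefficient, patient-cluster sandwich variance) was fitted with strata(transition) and again with transition × NYHA strata, with 1500 replicates per row. Information ratio = (mean Z without NYHA ÷ mean Z with NYHA)². For 1/2/4 this is (3.639/3.824)² = 0.906.

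| NYHA hazard II/III/IV | HR without / with NYHA | Shift in log HR | Information ratio | Power, HR 0.82 | Power, HR 0.87 |
|---|---|---|---|---|---|
| 1/1.25/1.6 | 0.822 / 0.822 | 0.0009 | 0.991 | 96.9% / 96.6% | 78.9% / 79.0% |
| 1/1.5/2.25 | 0.824 / 0.821 | 0.0029 | 0.971 | 96.9% / 96.9% | 78.2% / 79.3% |
| 1/2/4 | 0.828 / 0.820 | 0.0094 | 0.906 | 95.8% / 96.7% | 75.3% / 78.2% |
| 1/3/6 | 0.837 / 0.820 | 0.0198 | 0.807 | 95.0% / 96.6% | 71.0% / 79.2% |

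The Monte Carlo SE of the shift is at most 0.0003. Relative to |ln 0.82| = 0.198, the 1/2/4 shift is 0.0094/0.198 = 4.7%. With deaths at 50% of events the pattern is the same (0.826 against 0.819 for 1/2/4).

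**Where the loss comes from.** The mean robust SE is about 0.052 in both fits. The information ratio therefore reflects a smaller estimate, not a larger reported SE. That SE is also somewhat too large when allocation is balanced on a strongly prognostic NYHA class: 0.0519 against an empirical SD of 0.0500 (1/2/4), and 0.0516 against 0.0462 (1/3/6).

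**No true effect.** The mean log HR without NYHA lies between −0.0015 and 0.0017. Rejection without / with NYHA strata, in row order, is 5.4% / 5.7%, 4.1% / 4.7%, 3.7% / 5.1% and 3.7% / 5.7%.

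**Mechanism.** A large-sample check used a III:II ratio of 2.0, mix 50/48/2%, true HR 0.80 and 70% of events HF. Without NYHA, the first transition alone gave 0.805 and the pooled HF estimate 0.807. About half or more of the shift is thus ordinary omitted-covariate attenuation, already present before any selection on earlier HF events.

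**The case against.** The strongest reply is that little turns on this. The analysis is supportive, and the test of the objective is the first-event Cox model, which does stratify by NYHA class. SAP section 2 does not limit further analyses, so an adjusted version could be reported anyway. At weak to moderate NYHA effects the change in power is about one point or less. Part of the shift is a difference between a marginal and an NYHA-conditional hazard ratio, not an error. All of this stands, and it is why the priority is low.

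A reader might infer more than the documents support:

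- That the SAP breaches the protocol. The rule in protocol 11.5.1 on stratification variables describes the cause-specific Cox model; the recurrent analysis follows it with no covariates specified. This is an unexplained inconsistency, not a contradiction.
- That the loss is material whatever the NYHA effect. The documents give no NYHA mix and no NYHA hazard ratio; they say only that NYHA class is an expected predictor.
- That this is the only analysis using repeat HF events. Secondary objective #7 (SAP 4.4.7) sums readmissions over a patient's several index HF admissions, with NYHA class as a covariate.
- That adding NYHA makes the result comparable with the first-event result. The recurrent code fits one coefficient across HF and death transitions, so the estimand still differs.
- That NYHA strata remove the selection. With unmeasured patient frailty of variance 1, the limiting HR is about 0.853 against a true 0.82 even with NYHA strata.

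**Conclusion.** The point holds as a free improvement of low priority. The recurrent-event model drops a randomisation factor that the SAP expects to be prognostic, without a stated reason. If aCRT has a true effect, the hazard ratio is pulled slightly toward 1, partly by ordinary omitted-covariate attenuation and partly by selection into later transitions. If NYHA class is strongly prognostic, the robust test is also slightly conservative. There is no bias under the null and no inflation of type I error.

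The size rests on the assumed NYHA effect. Weak to moderate effects cost about 1–3% of the information. A III:II ratio of about 2 costs about 9–10%, and at a true HR of 0.87 that is 75.3% against 78.2% power. Only the extreme case (1/3/6) costs close to 20%.

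**What to change.** In SAP 4.4.2, remove NYHA stratification from the sentence listing what the recurrent-event analysis leaves out, and state that the model will account for NYHA class at enrollment. In the R line, replace strata(transition) with strata(transition, NYHA).

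Name the fallback in advance: if NYHA IV cells are sparse, enter NYHA as a covariate or combine classes III and IV. With 2% of patients in class IV, and under the mechanism check's other assumptions (85% event-free at 2 years, hazard doubled after a first HF event), those cells would hold only about 14 second and 5 third HF events at the final analysis.

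Keep cluster(pt). Clustering by site is a separate change that was not tested and is not needed here.

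The cost is one sentence and one term of code, with no new data. The same R line needs a correction in any case, because the parenthesis of Surv() closes before the status variable.

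### The recurrent HF-event model shares one treatment coefficient across HF and death transitions, so it returns an average of the two effects rather than a comparison of HF intervention rates

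*SAP*

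**What the plan says.** **Purpose.** Protocol 11.5.1 adds to the HF objective that "recurrent event survival analysis will be performed to compare rates of interventions for heart failure decompensation". SAP 4.4.2 says that "the incidence of intervention for heart failure decompensation will be summarized and compared between the two treatment arms using a multistate Markov model". Both name HF intervention only.

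**Model.** SAP 4.4.2 continues: "The multi-state model stratifies a Cox model by transition states as follows". In the formula that follows, the baseline hazard carries the transition index k and the coefficient vector β does not. The listed transitions include "second intervention for HF decompensation, etc., death, death after first intervention of HF decompensation".

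**Data.** For the example dataset the SAP states "A subject from R can transition to H1 (R->H1) or D (R->D"), and likewise from H1 to H2 or D. Example subject M0000003 contributes a death on an R->D row with Status=1.

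**Code.** The call opens "fit1 <- coxph(Surv(time1, time2), status) ~ factor(trtGroup) + cluster(pt") and ends with "strata(transition), data= mmsurvdata"). It has no treatment-by-transition term and no restriction to HF rows. On coding, "trtGroup indicates whether the subject is aCRT ON (trtGroup =1) or aCRT OFF (trtGroup =2").

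**The concern.** The purpose and the model do not match. Giving each transition its own baseline hazard does not give it its own treatment effect. With one coefficient over R->H1, H1->H2, R->D and H1->D rows, deaths count towards the estimate in the same way as HF events. The result is closer to a recurrent version of the composite primary endpoint than to its HF component.

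The number would nevertheless be reported as the recurrent HF result. Table 2 in SAP 4.1.3 schedules it for the interim DMC reports and the final report. SAP 4.2 says that an early-stopping assessment balances the primary objective with secondary objectives #1 (mortality) and #2 (HF events). A DMC weighing HF evidence against mortality would be looking at a figure that already contains mortality.

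**Working it through.** The documents give no figure for this analysis, so there is none to reproduce. The check is of what the specified model estimates.

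**1. Approximation.** Let d be the share of modelled transitions that are deaths. The shared coefficient is roughly

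log HR(pooled) ≈ (1 − d) × log HR(HF) + d × log HR(death).

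Example: HF 0.80, death 1.00, d = 0.17 gives 0.83 × ln 0.80 = 0.83 × (−0.2231) = −0.185, so HR ≈ 0.831.

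**2. Simulation.** The SAP's call was run in R with the bracket corrected, on 200,000 subjects per scenario in the SAP's R/H1/H2/D layout.

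- From Protocol 11.3.4: control event-free rate 85% at 2 years, so the hazard is −ln(0.85)/2 = 0.0813 per year; 4 years of accrual plus 3.5 more years of follow-up.
- Assumed, not in the documents: 15%, 30% or 45% of the initial control hazard is death; after a first HF event the HF hazard doubles and the death hazard is multiplied by 2.5; at most two HF events; exponential times.

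The fit returns one coefficient. Inverted to ON versus OFF:

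| True HF HR | True death HR | Death share d | Pooled HR, formula | Pooled HR, simulated | HF HR, separate coefficient |
|---|---|---|---|---|---|
| 0.80 | 1.00 | 0.17 | 0.831 | 0.838 | 0.803 |
| 0.80 | 1.00 | 0.33 | 0.861 | 0.876 | 0.810 |
| 0.80 | 1.00 | 0.49 | 0.892 | 0.897 | 0.809 |
| 1.00 | 0.80 | 0.14 | 0.969 | 0.970 | 1.004 |
| 1.00 | 0.80 | 0.29 | 0.937 | 0.942 | 1.002 |
| 1.00 | 0.80 | 0.44 | 0.907 | 0.906 | 1.002 |
| 0.80 | 1.25 | 0.19 | 0.871 | 0.875 | 0.800 |
| 0.80 | 1.25 | 0.36 | 0.939 | 0.936 | 0.793 |
| 0.80 | 1.25 | 0.51 | 1.004 | 0.993 | 0.801 |
| 0.82 | 0.82 | 0.16 | 0.820 | 0.815 | 0.816 |
| 0.82 | 0.82 | 0.31 | 0.820 | 0.815 | 0.825 |
| 0.82 | 0.82 | 0.46 | 0.820 | 0.813 | 0.805 |

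The pooled value tracks the HF effect only in the last three rows, where the two effects are equal. Separate coefficients recover the HF effect throughout.

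**3. Direction and syntax.** R takes the lowest factor level as reference, here 1 = ON, so the printed term is `factor(trtGroup)2`, OFF versus ON. In the first three rows it prints 1.194, 1.142 and 1.115, the reciprocals of the pooled values. SAP 4.3.2 codes `rand` as 1 = ON and 0 = OFF, and SAP 4.4.2 defines the HR as treatment compared with control. As typed, the call does not parse, because `Surv()` closes before `status`.

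**The case against.** **The main test is elsewhere.** Objective #2 is tested by a cause-specific Cox frailty model for first HF event, with Fine-Gray as a secondary analysis, and mortality has its own model. The recurrent analysis is additional and has no hypothesis or critical value of its own. This stands: a reader might infer that the objective's confirmatory result is compromised, and the documents do not support that.

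**The coefficient is not unrelated to HF.** A reader might infer that the model says nothing about HF events. That goes too far. The pooled value is close to the HF effect when deaths are few and equals it when the effects are equal, and the protocol hypothesises benefit on both components. The SAP also says openly that the model covers death. Including death transitions is sound. The difficulty is the shared treatment effect, and nothing in the plan establishes that the two effects are equal.

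**The code is only indicative.** It is introduced as an example. But the displayed formula has the same common β. A single β could carry separate effects if X were expanded by transition, but the SAP describes no such expansion and its dataset has one treatment column. The `cox.zph` check looks for time trends in the pooled coefficient and does not test whether HF and death effects agree.

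**The coding is a presentation matter.** This stands. Reversal gives a reciprocal with the same p-value. A reader might infer that this direction is opposite to every other analysis. The departure is from the HR convention in SAP 4.3.2 and 4.4.2; the KCCQ and EQ-5D mixed models put `rand` in CLASS with no reference stated, so by SAS default their printed solution is also OFF relative to ON. Nor would a true HF hazard ratio of 0.80 print as 1/0.80 = 1.25, because the call prints the reciprocal of the pooled value. The bracket error stops execution, so it cannot produce a wrong number.

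**Conclusion.** The point holds for the additional recurrent-event analysis only. As specified, it yields an event-weighted average of the HF and death log hazard ratios, not the comparison of HF interventions that both documents announce.

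The size depends on unequal effects and on the death share, which the documents do not give. Over assumed shares of about 14% to 51%, an HF hazard ratio of 0.80 with no death effect is diluted to about 0.84 to 0.90, and a pure mortality effect of 0.80 appears as about 0.97 to 0.91 with no HF effect present. If death moved the other way (1.25), an HF benefit of 0.80 would shrink to about 0.88 to 0.99. With equal effects there is no material distortion. The primary analysis and the main test of objective #2 are untouched. The correction is still worthwhile because the figure goes to the DMC and the final report.

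**What to change.** 1. In the SAP 4.4.2 formula, index β by transition type (to HF, to death).
2. In the code, replace the single treatment term with treatment-by-transition-type terms: one coefficient for all transitions to HF and one for all transitions to death. Keep the stratification by transition and the clustering by patient.
3. Report the HF coefficient as the recurrent-event result, with the death coefficient beside it.
4. Editorial: set aCRT OFF as the reference level, and write `Surv(time1, time2, status)`.

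The cost is a small edit to SAP text and code, and slightly lower precision than the pooled coefficient. The dataset layout is unchanged.
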